● is used to indicate a study procedure that requires documentation in the individual eCRF.

○ is used to indicate a study procedure that does not require documentation in the individual eCRF.

^a immunosuppressive or immunodeficient conditions.

Note: Details of COVID-19 infection-related signs and symptoms should also be recorded in a separate eCRF page.

*Number of days for recording of solicited events after each dose of study intervention is defined by Chinese authorities [NMPA, 2019a].

Table 3 Intervals between study visits for Co-administration group

Interval	Optimal interval	Allowed interval range	Allowed interval during special circumstances [#]
Visit 1→Visit 2	15 days	14-18 days between study enrolment and Dose 1 of IPV and Rotarix PCV-free	14-45 days
Visit 2→Visit 4	30 days	28-36 [†] days between Dose 1 of IPV and Rotarix PCV-free and Dose 2 of IPV and Rotarix PCV-free	28-60 days
Visit 4→Visit 6	30 days	28-36 [†] days between Dose 2 of IPV and Rotarix PCV-free and Dose 3 of IPV and BS for assessment of Rotavirus Ab, IgA	28-60 days
Visit 6→Visit 7	30 days	30-36 [†] days between Dose 3 of IPV and BS for assessment of anti-poliovirus types 1, 2 and 3 Ab	30-60 days

Ab: Antibody; BS: Blood sampling; IgA: Immunoglobulin A; IPV: Inactivated poliovirus vaccine; PCV: Porcine circovirus; PCV-free: no detection of PCV-1 and PCV-2 according to the limit of detection of the tests used

[†] Participants will not be eligible for inclusion in the Per Protocol Set for immunogenicity if they make the study visit outside this interval. Interval is computed as the difference between the 2 dates of the study procedure.

[#] Refer to Section 8 for more details on special circumstances (e.g., COVID-19 pandemic).

Table 4 Intervals between study visits for Staggered group

Interval	Optimal interval	Allowed interval range	Allowed interval during special circumstances [#]
Visit 1→Visit 2	15 days	14-18 [†] days between Dose 1 of Rotarix PCV-free and Dose 1 of IPV	14-45 days
Visit 1→Visit 3	30 days	28-36 [†] days between Dose 1 and Dose 2 of Rotarix PCV-free	28-60 days
Visit 2→Visit 4	30 days	28-36 [†] days between Dose 1 and Dose 2 of IPV	28-60 days
Visit 3→Visit 5	30 days	28-36 [†] days between Dose 2 of Rotarix PCV-free and BS for assessment of Rotavirus Ab, IgA	28-60 days
Visit 4→Visit 6	30 days	28-36 [†] days between Dose 2 and Dose 3 of IPV	28-60 days

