
 To evaluate the reactogenicity of Rotarix PCV-free and IPV in terms of solicited systemic events. To assess the safety of Rotarix PCV-free in terms of unsolicited AEs and serious adverse events (SAEs) and safety of IPV in terms of SAEs. 	
 Solicited AEs 
 For each solicited systemic event, percentage of participants reporting the occurrence of the event within 14 days (Day 1- Day 14) after Dose 1 and Dose 2 of Rotarix and IPV Unsolicited AEs 
 Percentage of participants reporting the occurrence of unsolicited AEs within 31 days (Day 1- Day 31) after each dose of Rotarix, according to the MedDRA classification. SAEs: 
 Percentage of participants reporting SAEs from the first dose of the study intervention up to study end in the Co-administration and Staggered groups.

Ab: Antibody; GMC: Geometric mean Ab concentration; GMT: Geometric mean Ab titer; IgA: Immunoglobulin A; IPV: Inactivated poliovirus vaccine; MedDRA: Medical Dictionary for Regulatory Activities; mL: milliliter; PCV: *Porcine circovirus*; SAE: Serious Adverse Event; U: Unit

*Seroconversion rate for IPV neutralizing Ab is defined as percentage of participants with

[figure not shown]
- Titer $\geq 1:8$ at 1 month after 3 dose primary schedule of IPV in participants with titer $<1:8$ pre-vaccination
- Titer ≥ 4 -fold increase in titer 1 month after 3 dose primary vaccination schedule in participants with titer $\geq 1:8$ pre-vaccination.

Note: the 4-fold increase will take into consideration the expected decline in maternal antibodies with estimated half-life of 28 days.

**Seroconversion rate for anti-RV IgA Ab is defined as the percentage of participants who were initially seronegative (i.e., with anti-RV IgA Ab concentration <20 U/mL prior the first dose of *Rotarix*) and developed anti-RV IgA Ab concentration ≥ 20 U/mL at 1 month post Dose 2.

** complementary details on estimand including impact of intercurrent events on the analysis is available in Section 3 and Section 4.

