4.5. Safety Analyses

The analyses will be descriptive and conducted on the ES.

The following calculations will be performed for each group:

- The percentage of doses and participants reporting at least 1 AE (solicited or unsolicited) during the 14-day (Day 1 to Day 14) solicited follow-up period will be computed, along with exact 95% CI. The same calculations will be done for AEs (solicited or unsolicited) rated as grade 3 in intensity and for AEs leading to a medically attended visit.
- The percentage of doses over the study and the percentage of participants (by dose and over the study) reporting each individual solicited systemic event will be computed, over the 14-day (Day 1 to Day 14) solicited follow-up period, following study intervention administration, along with exact 95% CI. The same calculations will be done for each individual solicited systemic event rated as grade 3 (grade 3 or grade 4 for fever) in intensity and events leading to a medically attended visit. Temperature above specific thresholds will also be summarized with threshold defined by half degree increment.

Note: Intensity of fever will be assessed by considering the grading scales recommended by the Chinese authorities [NMPA, 2019].

- The verbatim reports of unsolicited AEs will be reviewed by a physician and will be coded according to MedDRA. Every verbatim term will be matched with the appropriate Preferred Term. The percentage of participants with unsolicited AEs occurring within 31-day (Day 1 to Day 31) follow-up period after any dose of *Rotarix* PCV-free with its exact 95% CI will be tabulated by Preferred Term. The same calculations will be done for each AE rated as grade 3 in intensity, for AEs leading to a medically attended visit and for AEs causally related to HRV as per the investigator assessment.
- The percentage of participants reporting the occurrence of SAEs (any, related, fatal, fatal related) from Dose 1 of the study intervention up to study end with its exact 95% CI will be tabulated by study group and by preferred term.
- The percentage of participants reporting the occurrence of SAEs (any, related, fatal, fatal related) within 31-day (Day 1 to Day 31) follow-up period after any dose with its exact 95% CI will be tabulated by study group and by preferred term.
- SAEs and dropouts due to AEs will be described in detail.

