6.2.6. Onset day

The onset day for an event (e.g., AE, medication, vaccination) is the number of days between the last study vaccination and the start date of the event. This is 1 for an event occurring on the same day as a vaccination (and reported as starting after vaccination).

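### SAP 6.2.6 dates events from the last vaccination of either product, so in the Staggered group the onset day does not identify Days 1-31 after a Rotarix dose

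*Protocol*

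**What the plan says.** **Onset rule.** SAP 6.2.6 says that the onset day of an event (AE, medication or vaccination) "is the number of days between the last study vaccination and the start date of the event", with the vaccination day as Day 1. It names no product, and the SAP gives no other onset-day rule.

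**Windows.** The endpoints are tied to products.
- Unsolicited AEs: SAP 4.5 tabulates those "occurring within 31-day (Day 1 to Day 31) follow-up period after any dose of" Rotarix PCV-free. Protocol Table 11 and section 10.3.4 confirm that unsolicited AEs are collected only after Rotarix. IPV has no unsolicited window.
- Solicited events: the endpoint is occurrence "within 14 days (Day 1- Day 14) after Dose 1 and Dose 2 of Rotarix and IPV" (SAP 1.1).

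**Schedule.** In Staggered (Protocol 1.3, Table 4, repeated as SAP Table 5) the allowed ranges are:
- Visit 1 to Visit 2: 14-18 "days between Dose 1 of Rotarix PCV-free and Dose 1 of IPV"
- Visit 1 to Visit 3: 28-36 "days between Dose 1 and Dose 2 of Rotarix PCV-free"
- Visit 2 to Visit 4: 28-36 "days between Dose 1 and Dose 2 of IPV"
- Visit 4 to Visit 6: 28-36 "days between Dose 2 and Dose 3 of IPV"

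In Co-administration (Protocol Table 3) it is 28-36 "days between Dose 1 of IPV and Rotarix PCV-free and Dose 2 of IPV and Rotarix PCV-free", and the next interval, to IPV Dose 3, has the same range.

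Neither document says that a window closes at the next dose. Neither says how to assign an event that lies in both a Rotarix and an IPV window.

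**The concern.** An onset day counted from the last vaccination of any kind and a window counted from Rotarix agree only when no other product is given inside the window. In Staggered an IPV dose always is. An event on Rotarix Day 20 carries IPV onset day 5 on the optimal schedule, and nothing in that value says where it lies relative to Rotarix.

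If the 31-day table were built from this variable and restricted to events whose last vaccination was Rotarix, about half of each Staggered window would drop out. No IPV unsolicited table exists to receive those events. The Staggered Rotarix AE rate would then be too low, and Co-administration would look relatively worse in the safety description that the study is meant to provide.

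**Working it through.** **1. The plan's own calendar.** The optimal intervals put Visits 2, 3, 4, 5, 6 and 7 at 15, 30, 45, 60, 75 and 105 days after Visit 1. With 30-day months, 105/30 = 3.5, which matches the stated duration of about 3.5 months.

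**2. Gaps between consecutive doses in Staggered.** Let a = Visit 1 to 2 (14-18), b = Visit 1 to 3 (28-36) and c = Visit 2 to 4 (28-36). Table 4 does not state the Visit 2 to 3 or Visit 3 to 4 gap, so both are derived.

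| Gap | Formula | Minimum | Maximum | Optimal |
|---|---|---|---|---|
| Rotarix 1 to IPV 1 | a | 14 | 18 | 15 |
| IPV 1 to Rotarix 2 | b - a | 28 - 18 = 10 | 36 - 14 = 22 | 15 |
| Rotarix 2 to IPV 2 | a + c - b | 14 + 28 - 36 = 6 | 18 + 36 - 28 = 26 | 15 |
| IPV 2 to IPV 3 | stated | 28 | 36 | 30 |

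**3. The 31-day Rotarix window.** With Day 1 as the dose day, a gap of g days leaves Days 1 to g before the next vaccination. A 31-day window is free of another dose only if g is at least 31.
- Staggered, after Rotarix Dose 1: 14-18 days come before the IPV visit, and 31 - 18 = 13 to 31 - 14 = 17 days fall on or after it.
- Staggered, after Rotarix Dose 2: 6-26 days come before the IPV visit, and 31 - 26 = 5 to 31 - 6 = 25 days fall on or after it.
- Optimal schedule: 15 days before, and 31 - 15 = 16 days (Days 16-31) on or after. Day 31 of the first window is also the day of Rotarix Dose 2.
- Co-administration: only gaps of 28-30 days matter, with 31 - 30 = 1 to 31 - 28 = 3 days affected (1 day at the optimal 30). After Dose 1 the next visit is again a Rotarix visit, so those events still follow a Rotarix dose.

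**4. What the onset day can tell a programmer.** Take the optimal schedule after Rotarix Dose 2. Rotarix Day 31 has onset day 31 - 15 = 16, and Rotarix Day 32 has 32 - 15 = 17. The first is inside the window and the second outside, but a limit of 31 on the onset day passes both.

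**5. The 14-day solicited windows.** These overlap the next dose only if the gap is under 14 days, which is impossible after Rotarix Dose 1 (at least 14) and IPV Dose 2 (at least 28). Assume, for scale only, that all allowed dates are equally likely.
- After IPV Dose 1, b - a < 14 in 0 + 1 + 2 + 3 + 4 = 10 of 5 x 9 = 45 combinations, or 22%.
- After Rotarix Dose 2, a + c - b < 14 in 36 + 28 + 21 + 15 + 10 = 110 of 5 x 9 x 9 = 405 combinations, or 27%.
- Both cannot happen in one participant: b - a < 14 would then require c < 28. So 22.2% + 27.2% = 49% of schedules have one overlap.

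On the optimal 15-day spacing there is none. In Co-administration the gap is at least 28 days, so there is none either.

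**The case against.** The strongest reply is that SAP 6.2.6 is only a general descriptor and SAP 4.5 is the rule that selects events. Section 4.5 names Rotarix where Protocol 9.4.1 says only any dose, which shows the intended anchor. In Staggered, unsolicited AEs are recorded from Visit 1 to Visit 5 with no break at the IPV visits. Even on a literal reading, the event on Rotarix Day 20 has onset day 5, which lies within 1-31. It is lost only if someone also filters on the product last given, and no text asks for that.

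Much of this stands. A reader might infer that Staggered follow-up is cut short or that the Rotarix rate will be understated. The documents support neither as fact, because collection continues and no window is said to close. What the reply does not remove is that the only stated onset-day rule cannot produce the window that 4.5 asks for (step 4). A programmer must depart from 6.2.6 to do it correctly.

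A reader might also infer that overlapping solicited days are taken from the earlier dose. That is not supported. SAP 6.2.4.2 derives solicited events from an occurrence flag for a specific vaccination and its own period, without using 6.2.6.

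Counting an event in every window that it falls in has a cost too. One event would then count against two doses in the per-dose percentages, mainly in Staggered, so that counting needs a stated limit.

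**Conclusion.** The point holds as a conflict between SAP 6.2.6 and the Rotarix-specific window in the endpoint and SAP 4.5. In Staggered every 31-day Rotarix window contains an IPV dose. The onset day as defined refers to IPV or a later dose for 13-17 days after Rotarix Dose 1 and 5-25 days after Dose 2 (16 of 31 on the optimal schedule). Whether events are actually dropped or misplaced depends on 6.2.6 being used to place them. The effect on AE rates cannot be sized, because the documents give no expected rates.

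Two stronger readings should be avoided. The problem is not confined to Staggered, since Co-administration can be affected by 1-3 days, but it is almost entirely there. It also does not extend to IPV follow-up in general: IPV has no unsolicited window, and among its 14-day windows only the one after Dose 1 can overlap the next dose. The 22% and 27% figures rest on equally likely visit dates and describe overlap, not lost data.

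Only descriptive safety summaries are affected. SAEs from first dose to study end, immunogenicity, the primary non-inferiority test and its power are untouched. The change is still worth making before programming, because it is cheap and the possible distortion is nearly one-sided.

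**What to change.** Amend the SAP as follows:
- **6.2.6:** derive two onset days for each AE and medication, one from the most recent Rotarix dose and one from the most recent IPV dose, each with the dose day as Day 1.
- **4.5:** use the Rotarix-anchored day for the 31-day unsolicited AE tables, including the Grade 3, medically attended and HRV-related versions.
- **Overlap:** state that an event in overlapping windows counts in each product-specific table but only once in any-event summaries at participant level. Footnote the per-dose percentages for overlap, given that SAP 6.1.5 defines a dose as a vaccination visit.

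With Rotarix as the anchor, an IPV visit no longer shortens the Rotarix window in either group. Where the two Rotarix doses are 28-30 days apart, the last 1-3 days after Dose 1 are dated from Dose 2 and still count as after a Rotarix dose.

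The cost is one derived variable per product, a few sentences and a table footnote. Visits, data collection and sample size do not change.

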2. INTRODUCTION

2.1. Study rationale

GSK's *Rotarix* liquid vaccine is currently approved in all EEA countries, UK, US, Japan, as well as over 90 other countries. GSK intends to register *Rotarix* PCV-free liquid vaccine (hereafter referred as *Rotarix* PCV-free) in China. "PCV-free" is defined as no detection of PCV-1 and PCV-2 according to the limit of detection of the tests used.

In China, under the NIP, a 3-dose primary vaccination against poliovirus is currently recommended during the first year of life in a 2, 3 and 4 months of age schedule and a booster vaccine is recommended at 4 years of age. IPV is used for the first 2 doses, and OPV is used for the third and the fourth dose.

This study is designed to evaluate the immunogenicity and safety of IPV when co-administered with *Rotarix* PCV-free, in healthy Chinese infants.

2.2. Background

RV infects almost every child before they reach the age of 3 to 5 years and is the leading cause of acute gastroenteritis (GE) and diarrhea, which can lead to severe dehydration [Atherly, 2009]. Prior to the introduction of RV vaccines in 2006, RV was accountable for an estimated 528 000 deaths worldwide annually, with the largest number of deaths occurring in the Sub-Saharan Africa region [WHO position paper, 2021; Tate, 2016; Bányai, 2018]. In 2013, several years after the launch of RV vaccines, it has been estimated that approximately 215 000 deaths (95% confidence interval [CI]: 197 000, 233 000) were caused by RV infection. India, Nigeria, Pakistan, and Democratic Republic of Congo accounted for approximately half (49%) of all the estimated RV deaths in 2013 [Dennehy, 2008; Tate, 2016]. In China, 42.6% of all the hospitalizations for severe GE, 32.5% of outpatient visits for diarrhea and 9.3% of all diarrhea episodes in community settings are caused by RV [Fu, 2018].

The World Health Organization (WHO) recognizes RV vaccination as an effective measure to prevent RV infection and to reduce disease burden, and recommends its inclusion into all national infant immunization programs, particularly in countries where RVGE-associated fatality rates are high among children aged <5 years (e.g., South and South-Eastern Asia and Sub-Saharan Africa) [WHO position paper, 2021].

GSK HRV vaccine (*Rotarix*) is registered in around 130 countries and more than 790 million doses of the vaccine (lyophilized and liquid formulations) are estimated to have been distributed worldwide from its launch until July 2022.

Please refer to the current investigator's brochure (IB) for information regarding the preclinical studies, clinical studies and epidemiology studies of *Rotarix* vaccine.

2.3. Benefit/Risk assessment

Detailed information about the known and expected benefits and risks and expected adverse events of *Rotarix* can be found in the IB and of IPV can be found in the Prescribing Information (PI).

3. OBJECTIVES, ENDPOINTS, AND ESTIMANDS

Table 5 Study objectives, endpoints and estimands

Objectives	Endpoints and estimands
Primary (Confirmatory)	

 To demonstrate the immunological non-inferiority of IPV when co-administered with Rotarix PCV-free compared with IPV administered alone. 	
 Anti-poliovirus types 1, 2 and 3 neutralizing Ab seroconversion rate* 1 month post Dose 3 of IPV in the Co-administration and Staggered groups.
Secondary (Descriptive)	

 To evaluate the immunogenicity of IPV when co-administered with Rotarix PCV-free and when administered alone. 	
 Anti-poliovirus types 1, 2 and 3 neutralizing Ab GMTs at 1 month post Dose 3 of IPV in the Co-administration and Staggered groups. Percentage of participants with anti-poliovirus types 1, 2 and 3 neutralizing Ab titers $\geq 1:8$ and $\geq 1:64$ at 1 month post Dose 3 of IPV in the Co-administration and Staggered groups.

 To evaluate the immunogenicity of Rotarix PCV-free when co-administered with IPV and when administered alone. 	
 Anti-RV IgA Ab seroconversion rate** 1 month post Dose 2 in the Co-administration and Staggered groups. Anti-RV IgA Ab GMCs at 1 month post Dose 2 of Rotarix PCV-free in the Co-administration and Staggered groups. Percentage of participants with anti-RV IgA Ab concentrations ≥ 90 U/mL at 1 month post Dose 2 of Rotarix PCV-free in the Co-administration and Staggered groups.

 To evaluate the reactogenicity of Rotarix PCV-free and IPV in terms of solicited systemic events. To assess the safety of Rotarix PCV-free in terms of unsolicited AEs and serious adverse events (SAEs) and safety of IPV in terms of SAEs. 	
 Solicited AEs 
 For each solicited systemic event, percentage of participants reporting the occurrence of the event within 14 days (Day 1- Day 14) after Dose 1 and Dose 2 of Rotarix and IPV Unsolicited AEs 
 Percentage of participants reporting the occurrence of unsolicited AEs within 31 days (Day 1- Day 31) after each dose of Rotarix, according to the MedDRA classification. SAEs: 
 Percentage of participants reporting SAEs from the first dose of the study intervention up to study end in the Co-administration and Staggered groups.

Ab: Antibody; GMC: Geometric mean Ab concentration; GMT: Geometric mean Ab titer; IgA: Immunoglobulin A; IPV: Inactivated poliovirus vaccine; MedDRA: Medical Dictionary for Regulatory Activities; mL: milliliter; PCV: *Porcine circovirus*; SAE: Serious Adverse Event; U: Unit

*Seroconversion rate for IPV neutralizing Ab is defined as percentage of participants with

- Titer $\geq 1:8$ at 1 month after 3 dose primary schedule of IPV in participants with titer $< 1:8$ pre-vaccination
- Titer ≥ 4 -fold increase in titer 1 month after 3 dose primary vaccination schedule in participants with titer $\geq 1:8$ pre-vaccination.

Note: the 4-fold increase will take into consideration the expected decline in maternal antibodies with estimated half-life of 28 days.

**Seroconversion rate for anti-RV IgA Ab is defined as the percentage of participants who were initially seronegative (i.e., with anti-RV IgA Ab concentration < 20 U/mL prior the first dose of *Rotarix*) and developed anti-RV IgA Ab concentration ≥ 20 U/mL at 1 month post Dose 2.

Refer to Section 8 for details on SAEs.

Refer to Section 9.3 and Section 9.4 for additional details on statistical analyses.

[figure not shown]
Details related to attributes of estimand covering intercurrent events, population and treatment definition are provided in the Section 9.

4. STUDY DESIGN

4.1. Overall design

The study design is presented in [Figure 1](#).

Figure 1 Study design overview

AE: Adverse Event; IPV: Inactivated poliovirus vaccine; PCV: *Porcine circovirus*; PCV-free: no detection of PCV-1 and PCV-2 according to the limit of detection of the tests used; SAE: Serious Adverse Event; N: Total number of participants planned to be enrolled; n: Planned number of participants in each group.

Study interventions: IPV (Co-administered vaccine) and *Rotarix* PCV-free (Study vaccine).

[§] Refer to the Schedule of activities (SoA; Section 1.3) for Co-administration group. Note: For the Co-administration group, unsolicited AEs will be collected from visit 2 till visit 6.

+ Visit not applicable for participants in the Co-administration group.

[^] Blood sampling to be done before study intervention administration.

° Blood sample for anti-poliovirus types 1, 2 and 3 antibodies measurement.

* Blood sample for anti-RV IgA antibody measurement.

- **Experimental design:** Phase III, open-label, randomized, controlled study with 2 groups (see [Figure 1](#)).
- **Duration of the study:** The total duration of the study, per participant, will be approximately 3.5 months.
- **Control:** active comparator, i.e., staggered administration of licensed IPV and *Rotarix* PCV-free.
- **Blinding:** Open-label. Refer to Section [6.3.4](#) for details.
- **Data collection:** Standardized electronic Case Report Form (eCRF). Solicited systemic events will be collected using a diary card. Refer to Section [10.3.6.1](#) for details on recording and follow-up of SAEs.
- **Primary Completion Date (PCD):** Visit 7 (Month 3.5).
- **End of Study (EoS):** EoS is defined as last subject last visit (LSLV) (Visit 7) or date of the last testing/reading released of the Human Biological Samples, related to primary and secondary endpoints, whichever occurs later. EoS must be achieved no later than 8 months after LSLV. EoS cannot be before LSLV. Refer to Section [4.4](#) for details.

Table 6 Study groups, intervention and blinding

Study groups	Number of participants	Age (Min-Max)	Study interventions	Blinding
Co-administration	200	6-10 weeks*	IPV, Rotarix PCV-free	Open-label
Staggered	200	6-10 weeks*	IPV, Rotarix PCV-free	Open-label

IPV: Inactivated poliovirus vaccine; Max: maximum; Min: minimum; PCV: *Porcine circovirus*

* 6-10 weeks at the time of study enrolment

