Recording of administered intervention number	●	●	●	●		●		
Recording of regurgitation/vomiting		●		●				If regurgitation or vomiting occurs within 30 minutes after study intervention administration, administration of a replacement dose is not recommended. This information on regurgitation or vomiting should be recorded in the eCRF. The participant should continue to participate in the study
Distribution of 'Participant card'	0							See Section 8.3.5 for more information
Distribution of diary cards	●	●	●	●				
Laboratory Assessment								
Blood sampling for antibody determination (at least 2 mL)	● [^]				●		●	[^] Blood sampling before study intervention administration. Volume of the blood sample should be between 2 and 2.5 mL See Section 8.1.1 for more information
Safety assessments								
Record any concomitant medications/vaccinations	●	●	●	●	●	●	●	See Section 6.8 for more information
Recording of solicited events post Dose 1 and Dose 2 of study intervention (Days 1-14*)	●	●	●	●	●			See Section 10.3.3 and Section 10.3.6.1 for more information
Recording of unsolicited AEs after each dose of Rotarix administration (Days 1-31)	●	●	●	●	●			See Section 10.3.4 and Section 10.3.6.1 for more information
Record any intercurrent medical conditions ^a	●	●	●	●	●	●	●	See Section 9 for more information

CONFIDENTIAL

218485 (ROTA-098)
Protocol Amendment 1 Final

Age at time of study enrolment	6-10 weeks							Notes
	Visit 1	Visit 2	Visit 3	Visit 4	Visit 5	Visit 6	Visit 7	
Type of contact	Day 1	Month 0.5	Month 1	Month 1.5	Month 2	Month 2.5	Month 3.5	
Recording of AEs that led to withdrawal from study	●	●	●	●	●	●	●	See Section 10.3.6.1 for more information.
Recording of SAEs	●	●	●	●	●	●	●	See Section 10.3.6.1 for more information
Recording of SAEs related to study participation, or to a concurrent GSK medication/vaccine	●	●	●	●	●	●	●	See Section 10.3.6.1 for more information. The collection and reporting periods start once the participants' parents/LARs informed consent is obtained.
Return of diary cards		●	●	●		●		
Diary cards transcription by investigator or designee		●	●	●	●	●		
Study Conclusion							●	See Section 4.4 for more information

AE: Adverse Event; IPV: Inactivated poliovirus vaccine; LAR: Legally Acceptable Representative; PCV: *Porcine circovirus*; PCV-free: no detection of PCV-1 and PCV-2 according to the limit of detection of the tests used; SAE: Serious Adverse Event; mL: milliliter

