9.4. Analysis of safety

Safety analysis will be performed on the ES.

Participants who missed reporting events (solicited/unsolicited AEs or concomitant medications) will be treated as participants without the events (solicited/unsolicited AEs or concomitant medications, respectively).

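### Unsolicited AE recording can close at Day 29 or 30 after Rotarix Dose 2, although the endpoint window runs to Day 31

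*Protocol*

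**What the plan says.** **Endpoint.** Protocol Table 5 (Section 3) gives "Percentage of participants reporting the occurrence of unsolicited AEs within 31 days (Day 1- Day 31) after each dose of" Rotarix. SAP 4.5 analyses the same window. The unsolicited AE rows in the schedules of activities (Protocol 1.3, Tables 1 and 2) are also labelled for Days 1 to 31.

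**End of recording.** For Co-administration, the Figure 1 note states "For the Co-administration group, unsolicited AEs will be collected from visit 2 till visit 6". Table 1 agrees, with marks at Visits 2 to 6 and none at Visit 7. For Staggered, Table 2 has marks at Visits 1 to 5 and none at Visits 6 or 7.

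**Timing of the closing visit.** Protocol Tables 3 and 4 allow 28 to 36 days, with 30 optimal, from Rotarix Dose 2 to Visit 6 (Co-administration) and to Visit 5 (Staggered). The counting rule is "Interval is computed as the difference between the 2 dates of the study procedure". SAP 6.2.6 sets the onset day: "This is 1 for an event occurring on the same day as a vaccination".

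**Unreported events.** Protocol 9.4: "Participants who missed reporting events (solicited/unsolicited AEs or concomitant medications) will be treated as participants without the events". SAP 4.1.2 has the same rule.

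**The concern.** The window is stated in days and recording is stated in visits, and the two do not always meet. An infant whose closing visit is at the early end of the allowed interval is not a protocol deviation, yet the marked recording stops before Day 31.

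Protocol 10.3.4 sends events that are neither medically attended nor a worry to the parents to an interview at the next visit. After the closing visit, no later visit is marked for unsolicited AEs. Because an unreported event counts as no event, a missed late event does not show up as missing data. It lowers the reported percentage. Sites could also differ: some may follow the Days 1 to 31 label and record late events, while others stop at the last mark.

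**Working it through.** **Inputs**
- Window: Day 1 to Day 31 after each Rotarix dose (Protocol Table 5, SAP 4.5).
- Interval from Rotarix Dose 2 to the closing visit: 28 to 36 days, optimal 30, in both groups (Protocol Tables 3 and 4). Under special circumstances it is 28 to 60 days, so the lower limit is unchanged.
- Day numbering: dosing day = Day 1; intervals are date differences. Hence day of visit = interval + 1.

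**Step 1. The plan's own figure.** At the optimal interval, 30 + 1 = Day 31. The nominal schedule matches the stated window.

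**Step 2. The allowed range.** Days without a marked collection point = max(0, 31 − (interval + 1)).

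| Interval (days) | Visit falls on | Days left uncovered |
|---|---|---|
| 28 | Day 29 | 2 |
| 29 | Day 30 | 1 |
| 30 | Day 31 | 0 |
| 31 to 36 | Day 32 to 37 | 0 |

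Two of the nine allowed intervals close recording early.

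**Step 3. Size**
- Largest loss: 2/31 = 6.5% of the Dose 2 window, or 2/62 = 3.2% of the two dose windows together.
- Average loss, assuming visits spread evenly over the nine allowed intervals: (2 + 1)/9 = 0.33 day, and 0.33/31 = 1.1% of the Dose 2 window.
- The documents give neither the distribution of visit dates nor AE rates, so the loss cannot be turned into percentage points of the endpoint.

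**Step 4. Dose 1.** In each group the closing visit is at least 28 + 28 = 56 days after Rotarix Dose 1, that is Day 57 or later. The Dose 1 window is covered.

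**Step 5. Would the next visit close the gap?** Within the normal allowed intervals:
- Co-administration Visit 7 falls between 28 + 30 + 1 = Day 59 and 36 + 36 + 1 = Day 73 after Rotarix Dose 2.
- Staggered Visit 6 falls between (14 + 28 + 28) − 36 + 1 = Day 35 and (18 + 36 + 36) − 28 + 1 = Day 63 after Rotarix Dose 2.

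Both are always after Day 31.

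**The case against.** **Late events do have some written routes.** Protocol 10.3.4 asks parents to contact the site as soon as possible about medically attended events and any others that concern them, independently of visits. SAEs and AEs leading to withdrawal are marked through Visit 7 in both groups, and SAP 6.2.4.3 includes SAEs in the unsolicited AE summaries. Concomitant medication is collected for Days 1 to 31 after each dose (Protocol 6.8), so some treated events could surface there. This stands. A reader might infer that nothing occurring after the closing visit can be captured, and the documents do not support that. What remains is the non-serious event that is neither medically attended nor worrying: its only route is an interview at a visit not marked for it. Protocol 10.3.6.3.1 does not help, because it concerns follow-up of AEs already documented.

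**The marks may be nominal.** The row label says Days 1 to 31, and the optimal visit lands on Day 31. One can read the marks as approximate and the label as governing. The timeline bars of Protocol Table 11 and the drawing in Figure 1 are not visible in the text I worked from, so I cannot say what they show. The point is therefore a conflict to reconcile as well as a gap. The Figure 1 note nevertheless ends collection at a visit in plain words.

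**Attribution in Co-administration.** SAP 6.2.6 counts onset from the last study vaccination. IPV Dose 3 is given at Visit 6, so after an early Visit 6 the remaining days would be numbered from IPV Dose 3. One could argue that Visit 6 is a natural boundary. The endpoint, however, is defined from each Rotarix dose. What stands is that a new mark alone may not place these events in the Rotarix Dose 2 window, so the SAP rule has to change too.

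**Recall.** A later question asks parents to remember one or two days from some weeks before, and for longer in one group than in the other. This is a fair cost and is counted under the fix.

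**Conclusion.** The point holds as a small mismatch between a stated endpoint window and the stated recording period. For compliant infants seen 28 or 29 days after Rotarix Dose 2, the last 2 or 1 days have no marked collection point. The loss is at most 6.5% of the Dose 2 window and about 1% on average under the even-spread assumption. The direction is downward, because unreported events count as absent. It concerns a descriptive secondary endpoint and does not touch the primary objective.

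Three stronger readings are not supported:
- A reader might infer that a visit at exactly 30 days also falls short. That visit is on Day 31, so the window is reached.
- A reader might want a number of affected infants. The documents do not say how many will be seen at 28 or 29 days, so any count would be a guess.
- A reader might infer a bias between the groups. The allowed interval to the closing visit is the same in both, so the length of the shortfall does not differ by design, and the documents give no event rates from which to claim another difference.

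**What to change.** 1. **Protocol 4.1, Figure 1 note:** replace the end point at Visit 6 with collection through Day 31 after Rotarix Dose 2.
2. **Protocol 1.3:** add an unsolicited AE mark at Visit 7 in Table 1 and at Visit 6 in Table 2. Limit it to events with onset up to Day 31 after Rotarix Dose 2, and require it only when the closing visit was before Day 31. Check that Table 11 agrees.
3. **SAP 6.2.6:** state that, for this endpoint, onset day is counted from the Rotarix dose and not from the last study vaccination. This is needed in Staggered as well, where IPV Dose 2 (Month 1.5) nominally falls about 15 days after Rotarix Dose 2 (Month 1).

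**Cost.** Two table marks, one reworded note, one sentence in the SAP, and one question at a visit that already takes place. No visit or procedure is added. The downside is recall. On the nominal schedule the question comes about 30 days after the window closes in Co-administration (60 − 30) and about 15 days in Staggered (45 − 30). That is slightly unequal in an open-label study, but it concerns only one or two days in infants seen early.
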